### 6.1.3 PRODUCT STORAGE AND STABILITY

The DCTclock hardware should be stored in a secure location. As with any electronic device, it should not be exposed to water or extreme temperatures. The standard ambient conditions commonly found in medical office workspaces are acceptable.

---

### 6.1.4 PREPARATION

The DCTclock system will be installed by the sponsor and will be ready to use without additional preparation by the study site.

---

### 6.1.5 ADMINISTRATION

See the Investigator's Brochure for detailed DCTclock test administration instructions. Administration instructions for the standard neuropsychological tests are detailed in the Study Reference Manual (SRM).

---

## 6.2 STUDY AGENT ACCOUNTABILITY PROCEDURES

DCTclock will be provided to the investigational site for use only in this study. The devices issued to each site will be logged. The site PI will be responsible for ensuring that the device is securely stored and used only accordance with the study protocol. DCTclock automatically logs the device information used to generate each test. The sponsor will ensure that all devices are collected and accounted for at the end of the study.

---

## 6.3 INDICATION FOR USE OF STUDY DEVICE

DCTclock is intended for use by clinicians as an adjunctive tool to evaluate cognitive function in adults aged 55-95. DCTclock, a digitized version of the standard pen and paper neuropsychological clock drawing test, is a non-invasive, computer-based cognitive assay.

---

# 7 STUDY PROCEDURES AND SCHEDULE

---

## 7.1 STUDY PROCEDURES/EVALUATIONS

Prior to initiating the study at a site, the protocol and informed consent form (ICF) will be approved by the reviewing Institutional Review Board (IRB) for the site. SRMs will be provided to each site to access all related study materials.

Site personnel involved in the study will be trained on the following items prior to administering any aspect of the study:

- Protocol
- Administration of all assessment tools
- Use of the DCTclock system
- Data collection forms

---

### 7.1.1 STUDY SPECIFIC PROCEDURES

- Demographics and review of medical history and current medications
- Assessment of impairment of the dominant hand
- Assessment of recreational drug or alcohol use
- Reading and comprehension assessment
- Hamilton-Veale Contrast Sensitivity
- DCTclock
- Purdue Peg Board
- MMSEworld
- MoCA
- Benton Judgement of Line Orientation\*
- Rey Complex Figure\*
- D-KEFs Verbal Fluency (sub-test of D-KEFs)\*
- Digit Span and Reliable Digit Calculation (sub-test of WAIS-IV)
- Block Designs (sub-test of WAIS-IV)\*
- Trail Making Test – Parts A and B
- Symbol Digit Modalities\*
- Geriatric Depression Scale (15 item version)\*

Assessments indicated with an asterisk (\*) above will only be given to participants who complete visit 1 under protocol version 1.

No results from these assessments will be provided to the participant.

## 7.2 LABORATORY PROCEDURES/EVALUATIONS

This study does not involve any laboratory procedures.

---

### 7.2.1 SPECIMEN PREPARATION, HANDLING, AND STORAGE

There are no specimens collected as part of this study.

## 7.3 STUDY SCHEDULE

### 7.3.1 SCREENING AND VISIT 1

#### Screening and Visit 1 (Day 1)

- Administrator #1 (consent, demographics + 14 min):
- Obtain informed consent of potential participant verified by signature on written informed consent form approved by the IRB. Eligible participants will be considered enrolled at the time of signing informed consent.
- Demographic information, medical history and current medication information collected.
- Screening tests and the DCTclock test will be administered in the following order:
  - Assessment of impairment of dominant hand- <1 min
  - Assessment of recreational drug and alcohol use- <1 min
  - Consent reading and comprehension assessment- 1 min
  - Hamilton-Veale Contrast Sensitivity test- 3 min
  - DCTclock test including demographics and recording of adverse device effects reported by participant or administrator- 3 min
  - Purdue Peg Board test- 5 min
- If a subject screen fails at any step, they will not complete the remaining assessments. Eligible subjects will then complete the study assessments.
- Administrator #2 (83 min for those who complete all assessments under version 1 of the protocol, 28 min for those who complete the bolded assessments below under version 2 of the protocol):
  - **MMSEworld- 10 min**
  - **MoCA- 8 min**
  - Benton Judgment of Line Orientation- 10 min
  - Rey Complex Figure- 15 min
  - D-KEFs Verbal Fluency Test- 10 min
  - **Digit Span and Reliable Digit Calculation - 5 min**
  - Block Designs- 10 min
  - **Trail Making Test A+B- 5 min**
  - Symbol Digit Modalities- 5 min
  - Geriatric Depression Scale (15 item version)- 5 min

### 7.3.2 VISIT 2 (FINAL STUDY VISIT)

#### Visit 2 (Day 8-29)

- Administrator #1 (14 min):
- Screening tests and the DCTclock test will be administered by Administrator # 1 in the following order:
  - Assessment of impairment of dominant hand- <1 min
  - Assessment of recreational drug and alcohol use- <1 min
  - Consent reading and comprehension assessment- 1 min
  - Hamilton-Veale Contrast Sensitivity test- 3 min
  - DCTclock test including demographics and recording of adverse device effects reported by participant or administrator- 3 min
  - Purdue Peg Board test- 5 min

If a subject screen fails at any step, they will not complete the remaining assessments. Eligible subjects will then complete the study assessments.

- Administrator #2 (83 min for those who complete all assessments under version 1 of the protocol, 28 min for those who complete the bolded assessments below under version 2 of the protocol):
  - **MMSEworld- 10 min**
  - **MoCA- 8 min**
  - Benton Judgment of Line Orientation- 10 min
  - Rey Complex Figure- 15 min
  - D-KEFs Verbal Fluency Test- 10 min
  - **Digit Span and Reliable Digit Calculation - 5 min**
  - Block Designs- 10 min
  - **Trail Making Test A+B- 5 min**
  - Symbol Digit Modalities- 5 min
  - Geriatric Depression Scale (15 item version)- 5 min

This visit ends the participant's participation in this study.

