### 5.2 PARTICIPANT EXCLUSION CRITERIA

- Ineligible for written informed consent as judged by >4 errors in reading the introductory paragraph of the consent form aloud while holding the text at the most comfortable viewing distance (typically 12-18", printed in Arial, size 14, character spacing expanded by 1 point and line spacing printed at 1.5) while wearing their customary corrective lenses. The text is as follows:
  - "You are being asked to join a research study because you are 55-95 years old and you are interested in evaluating a new assessment of your mental processing. In order to decide if you should participate in this study, you should know enough about the risks and benefits. This process is known as informed consent."
- Inability to answer three questions about testing after consent is read to the subject:
  - How long does each session take? (Correct response is approximately 60 or 110 mins per session.)
  - How many sessions are there? (Correct response is a total of two sessions.)
  - How much will you be getting paid? (Correct response is fifty dollars per session.)
- Assessment of impairment of the writing hand that precludes ability to perform the DCTclock test. The participant will be asked whether they have suffered any significant injury or other physical change in function that would prevent them from holding a pen and writing. An answer of 'yes' would be an exclusion criteria.
- Impaired manual dexterity in the writing hand as judged by timed performance below cut-off standards (quantified by Purdue Peg Board score < 6).
- Impaired vision of both eyes as judged by poor contrast sensitivity (quantified by Hamilton-Veale Contrast Sensitivity < 7).
- Under the influence of recreational drugs or alcohol at the time of the visit.
- Current or recent (within the last 6 months) participation in a clinical trial that includes the use of a drug or intervention to alter cognitive function.
- Recent (within the last 6 months) cognitive testing with MoCA, MMSE, or another Clock Drawing Test.
- Visit 2 Only:
  - Any self-reported change (addition or discontinuation) of the following medications between visit 1 and visit 2; Timolol (eye drop), Benadryl, beta blockers, steroids or over the counter medications for sleep (PM varieties).

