### 7.3.4 SCHEDULE OF EVENTS TABLE

Procedure	Screening/Visit 1	Visit 2	Administrator
Time	0	Within 1-4 weeks of visit 1	
Consent	X		1
Inclusion/Exclusion Criteria (Includes reading and comprehension assessments, dominant hand evaluation, and drug/alcohol use)	X	X	1
Hamilton-Veale Contrast Sensitivity	X	X	1
DCTclock Test and Demography	X	X	1
Assessment of adverse device effects	X	X	1
Purdue Peg Board	X	X	1
NP test battery:			

MMSEworld	X	X	2
MoCA	X	X	2
Benton Judgement of Line*	X	X	2
Rey Complex Figure*	X	X	2
D-KEFs Verbal Fluency*	X	X	2
Digit Span and Reliable Digit Calculation	X	X	2
Block Designs*	X	X	2
Trail Making Test	X	X	2
Symbol Digit Modalities*	X	X	2
Geriatric Depression Scale*	X	X	2

Assessments indicated with an asterisk (\*) above will only be given to participants who complete visit 1 under protocol version 1.

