#### 10.4.5 ANALYSIS OF SECONDARY EFFECTIVENESS ENDPOINTS

Participants will undergo cognitive testing with both the DCTclock and the reference standard, MMSE twice, where the second examination will be one to four weeks after the first examination. The secondary endpoints are DCTclock scores, MMSE scores and assessment of DCTclock and MMSE impaired and unimpaired status at each of two time points. The secondary analysis will assess the comparability of DCTclock test-retest reliability to that of MMSE. DCTclock test results of “unanalyzable” will be excluded from these analyses. Also, participants who no longer satisfy the inclusion/exclusion criteria prior to the second examination will also be excluded from this analysis.

Agreement analysis: For each of DCTclock and MMSE separately, the agreement between the first and second measurements will be carried out as follows:

1. A scatter plot of reading 2 vs. reading 1 will be generated, superimposed with a line of identity. An unweighted Deming regression (where the variance of the measurement error for each of DCTclock and MMSE is determined by the two measurements that were collected 1-4 weeks apart) will be carried out to determine the y-intercept, slope and their two-sided 95% confidence intervals. The correlation coefficient will also be determined. A hypothesis test of the slope vs. 1 and of the y-intercept vs. 0 will be carried out. Specifically, the following hypothesis test will be carried out:

$$H_0: \beta_0 = 0 \text{ vs. } H_1: \beta_0 \neq 0 \quad \text{and} \quad H_0: \beta_1 = 1 \text{ vs. } H_1: \beta_1 \neq 1$$

where  $\beta_0$  and  $\beta_1$  are the y-intercept and slope, respectively, from the Deming unweighted regression.

2. Within each of DCTclock and MMSE separately, participants will be categorized as impaired, not impaired or indeterminate/intermediate for each of the two measurements obtained on each participant. A 3-by-3 table, with the rows being the second reading status and with columns being the first reading cognitive status, will be generated as follows for each of DCTclock and MMSE:

		Reading 1			
Reading 2		Impaired	Indeterminate/Intermediate	Unimpaired	Total
	Impaired	a	b	c	a+b+c
	Indeterminate/intermediate	d	e	f	d+e+f
	Unimpaired	g	h	i	g+h+i
	Total	a+d+g	b+e+h	c+f+i	a+b+c+d+e+f+g+h+i

The following statistics will be calculated from the above table:

Positive Percent Agreement (PPA):  $a/(a+d+g)*100$  and its two-sided 95% Wilson confidence interval

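### The repeated comprehension screen at visit 2 gates entry to the second reading on cognition and can selectively remove impaired participants from the test-retest analysis

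*Protocol*

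**What the plan says.** Protocol 5.2 has two consent-related exclusions. One is a read-aloud test: "Ineligible for written informed consent as judged by >4 errors in reading the introductory paragraph of the consent form aloud". The other is comprehension: "Inability to answer three questions about testing after consent is read to the subject". The three questions cover session length, number of sessions and payment; the first reads "How long does each session take? (Correct response is approximately 60 or 110 mins per session". None of the answers is in the introductory paragraph that 5.2 prints for reading aloud.

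In the schedule table (7.3.4), the consent row is marked at visit 1 only. The row "Inclusion/Exclusion Criteria (Includes reading and comprehension assessments, dominant hand evaluation, and drug/alcohol use" is marked at both visits. The visit descriptions show the same split. Visit 1 is timed as "Administrator #1 (consent, demographics + 14 min" and visit 2 as "Administrator #1 (14 min". Both list a one-minute slot for the combined reading and comprehension check; at visit 2 it is "Consent reading and comprehension assessment- 1 min".

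The check comes before DCTclock and before everything given by the second administrator, MMSE included. Under 7.3.2 a fail at any step ends testing for that visit. For the reliability analysis, 10.4.5 adds that "participants who no longer satisfy the inclusion/exclusion criteria prior to the second examination will also be excluded from this analysis". Section 5.4.2 does not replace people who miss the second visit, and 10.4.1 allows no imputation.

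**The concern.** Aim 2 is the test-retest reliability of a cognitive test, in a sample of which half (200 of 400 evaluable, section 5.3) is sought from neurology clinics because those people are more likely to be impaired. A check of understanding has an obvious purpose before a signature is obtained. Repeated at visit 2 as a pass/fail step, it decides who supplies a second reading, and it does so on a trait close to the one being measured. The hand, contrast sensitivity, peg board, drug/alcohol and medication checks deal with other reasons why a second drawing might differ. The comprehension questions do not clearly do that.

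If those who fail are mostly the more impaired, the retest sample is narrower than the visit 1 sample. The impaired column of the reading 1 by reading 2 table then thins, and the ICC, weighted kappa and percent agreement for impaired describe a milder group than the one enrolled.

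**Working it through.** **1. Is the consent re-read at visit 2?** The protocol does not say, so the timings were checked. Taking each item given as under one minute as 1, the visit 2 steps for the first administrator are hand 1 + drug/alcohol 1 + reading and comprehension 1 + contrast sensitivity 3 + DCTclock 3 + peg board 5 = 14 minutes. This reproduces the stated total exactly. Visit 1 lists the same six steps and adds consent and demographics on top of the 14 minutes. The visit 2 total therefore has no time set aside for going through the consent again. The one-minute slot is the same length at both visits, although at visit 1 consent is timed separately.

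**2. What would the questions then test?** Visit 2 falls on Day 8 to 29, that is 7 to 28 days after Day 1. The printed paragraph does not contain the answers, so reading it aloud again does not supply them. On the scheduled timings, the comprehension half relies on what was learned at visit 1. The reading half does not.

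**3. What follows a fail?** No second DCTclock or MMSE (7.3.2), no place in the test-retest analysis (10.4.5), no replacement (5.4.2) and no imputation (10.4.1). The person stays in the Evaluable dataset, which requires DCTclock and MMSE testing but not a second visit (10.3). The ITT-versus-Evaluable comparison in 10.4.8 therefore does not isolate this loss.

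**4. How large could the effect be?** The protocol gives no visit 2 failure rate and no link between failing and cognitive status. Everything in this step is assumed.

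Model: 1,000,000 simulated participants; true score t standard normal; each reading = t + error with variance (1 − rel)/rel, for rel = 0.80 or 0.70; categories cut at the 30th and 70th percentiles of reading 1. Two failure patterns:
- Flat: 10%, 25% or 50% of the lowest 30% on t fail. Loss = 0.30 × 10%, 25%, 50% = 3%, 7.5%, 15%.
- Graded: probability of failing = 1/(1 + exp(4(t − m))), with m = −2, −1.5 or −1.

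Agreement for impaired is a/(a+d+g) × 100, as in 10.4.5. The correlation stands in for the ICC, because both readings have the same mean and variance in this model. Each cell gives rel 0.80 / rel 0.70.

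| Pattern | Lost | Correlation | Weighted kappa | Agreement for impaired (%) | Impaired at reading 1 (%) |
|---|---|---|---|---|---|
| None | 0% | 0.800 / 0.700 | 0.686 / 0.590 | 70.4 / 63.6 | 30.0 / 30.0 |
| Flat | 3.0% | 0.796 / 0.695 | 0.680 / 0.584 | 69.4 / 62.5 | 28.5 / 28.7 |
| Flat | 7.5% | 0.790 / 0.687 | 0.669 / 0.572 | 67.5 / 60.4 | 26.1 / 26.5 |
| Flat | 15.0% | 0.773 / 0.665 | 0.641 / 0.541 | 62.6 / 55.5 | 21.4 / 22.4 |
| Graded | 3.4% | 0.778 / 0.672 | 0.668 / 0.569 | 67.0 / 59.7 | 27.6 / 27.7 |
| Graded | 8.5% | 0.757 / 0.646 | 0.642 / 0.540 | 61.8 / 54.3 | 24.2 / 24.6 |
| Graded | 18.0% | 0.728 / 0.610 | 0.597 / 0.493 | 52.3 / 45.5 | 18.3 / 19.3 |

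Fall in weighted kappa: from 0.686 − 0.680 = 0.006 to 0.590 − 0.493 = 0.097. Fall in agreement for impaired: from 70.4 − 69.4 = 1.0 to 70.4 − 52.3 = 18.1 points.

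In counts, if all 400 evaluable participants otherwise returned and rel were 0.80, the impaired column would start at 400 × 0.30 = 120. It would end between 388 × 0.285 ≈ 111 (3% lost) and 328 × 0.183 ≈ 60 (18% lost).

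A second model used two equal source groups 1.6 SD apart, with failure depending on state at visit 2. Losses of 4%, 9% and 17% took weighted kappa from 0.70 to 0.68, 0.66 and 0.63, and agreement for impaired from 69% to 65%, 60% and 53%. Direction and range are the same.

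**The case against.** The strongest reply is that no section says the consent is not re-read. The item is called a consent reading, 5.2 puts the questions after the reading, the consent row in 7.3.4 could mean only the signature, and 13.3.2 treats consent as continuing through the study. The 14 minutes is built from rounded figures. This stands to the extent that non-re-reading is an inference, though one the timings support. It does not remove the point, because comprehension questions asked straight after a re-reading still admit people to reading 2 according to cognition.

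A reader might infer that the whole visit 2 check is a memory test. It is not. Reading aloud needs no recall and can fail for visual reasons. Returning participants have also sat one session, are attending the second, are paid per completed visit, and all passed the same screen at visit 1. That should keep failures down; it does not make them random.

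Excluding people whose state has changed between visits is a recognised choice in reliability studies, and the medication-change criterion in 5.2 serves it. Rechecking comprehension in a partly impaired sample also protects participants. Both arguments are fair. But if the information is not given again, the visit 2 questions are asked under different conditions from visit 1, and a fail need not show change.

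On visibility, 10.4.12 lists DCTclock and MMSE scores by time point, 14.1 requires the reason for discontinuation in the subject file, and a SAP could add a disposition table. It would be wrong to say that the loss cannot be seen. The protocol itself, however, plans no summary of it by reason and reading 1 status.

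**Conclusion.** The point holds as a risk of selective loss that the protocol creates and does not control. It is not a demonstrated bias. The screen recurs at visit 2, consent is scheduled at visit 1 only, and a fail removes the person from the second reading and from the reliability analysis.

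The size runs from trivial to material: about 0.01 to 0.10 on weighted kappa and about 1 to 18 points on agreement for impaired, for assumed losses of 3% to 18% concentrated in low scorers. These figures rest on the assumed reliability, category shares and failure patterns, none of which the protocol supplies.

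Three stronger readings are not supported:
- The impaired column is not emptied. Even the largest assumed loss leaves about 60 of 120.
- The effect does not flatter the device's absolute reliability. In both models, removal lowers the agreement statistics.
- The primary analysis is not touched, since 10.4.2 uses the first examination only.

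The sufficiency rule in 10.4.5 compares DCTclock with MMSE and the battery. DCTclock and MMSE lose the same people, so that comparison is less exposed than the absolute values, although the two need not be affected equally. What is most at stake is the absolute reliability estimate and how far it applies to impaired users.

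**What to change.** Reconcile 5.2, 7.3.2, 7.3.4 and 10.4.5 in one of two ways:

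- the comprehension questions are not a scored exclusion from the visit 2 tests and the retest analysis, and continuing willingness is confirmed in a way the IRB accepts; or
- the questions stay, and the consent information is given again immediately before them, with the step and its time written into the visit 2 schedule.

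Under either option, report visit 2 screen failures by reason, by reading 1 classification on DCTclock and on MMSE, and by recruitment source, next to the test-retest results. Under the second option some selection on cognition remains, and this table is what lets a reader judge it.

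The cost is an amendment to the wording and one extra table, plus either a few minutes at visit 2 or a less formal recheck of comprehension. Simply deleting the check, with nothing in its place, would be harder to defend in a sample that includes impaired people.

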### 7.3.3 EARLY TERMINATION VISIT

This study will not include an early termination visit.

### 7.3.4 SCHEDULE OF EVENTS TABLE

Procedure	Screening/Visit 1	Visit 2	Administrator
Time	0	Within 1-4 weeks of visit 1	
Consent	X		1
Inclusion/Exclusion Criteria (Includes reading and comprehension assessments, dominant hand evaluation, and drug/alcohol use)	X	X	1
Hamilton-Veale Contrast Sensitivity	X	X	1
DCTclock Test and Demography	X	X	1
Assessment of adverse device effects	X	X	1
Purdue Peg Board	X	X	1
NP test battery:			

MMSEworld	X	X	2
MoCA	X	X	2
Benton Judgement of Line*	X	X	2
Rey Complex Figure*	X	X	2
D-KEFs Verbal Fluency*	X	X	2
Digit Span and Reliable Digit Calculation	X	X	2
Block Designs*	X	X	2
Trail Making Test	X	X	2
Symbol Digit Modalities*	X	X	2
Geriatric Depression Scale*	X	X	2

Assessments indicated with an asterisk (\*) above will only be given to participants who complete visit 1 under protocol version 1.

#### 7.4 CONCOMITANT MEDICATIONS

There are no medication restrictions for this study outside of those listed in the exclusion criteria. A current medication list will be collected at visit 1.

### 8 ASSESSMENT OF SAFETY

#### 8.1 SPECIFICATION OF SAFETY PARAMETERS

Although this study involves an investigational device, there is a low risk of any physical injury to participants. Any reports of unanticipated adverse device effects (UADEs) will be collected at each use of the device and reviewed centrally for reportability.

##### 8.1.1 DEFINITION OF ADVERSE EVENTS (AE)

Adverse event means any untoward medical occurrence associated with the use of an intervention in humans, whether or not considered intervention-related (21 CFR 312.32 (a)).

##### 8.1.2 DEFINITION OF SERIOUS ADVERSE EVENTS (SAE)

An AE is considered serious if in the view of either the investigator or sponsor, it results in any of the following outcomes: death, a life-threatening AE, inpatient hospitalization or prolongation of existing

hospitalization, a persistent or significant incapacity or substantial disruption of the ability to conduct normal life functions, or a congenital anomaly/birth defect. Important medical events that may not result in death, be life-threatening, or require hospitalization may be considered serious when, based upon appropriate medical judgment, they may jeopardize the participant or subject and may require medical or surgical intervention to prevent one of the outcomes listed in this definition.

An unanticipated adverse device effect (UADE) means any serious adverse effect on health or safety or any life-threatening problem or death caused by, or associated with a device, if that effect, problem or death was not previously identified in nature, severity or degree of incidence in the investigational plan or application (including supplementary plan or application), or any other unanticipated serious problem associated with a device that relates to the rights, safety or welfare of subjects (21 CFR 812.3(s)).

